5.1 Treatment Group Sample

The treatment group sample is drawn from a list, prepared by each project, of all children aged 3.5 years and over, and their parents, who are the target of a *substantial and sustained* intervention. This list will be prepared by each project from which the evaluation team will then draw a random sample of 35. This will yield a total sample of 385 children and their parents.

The list of children and their parents prepared by each project will also indicate the childcare centres which are delivering the interventions and the member of staff in each centre who works most closely with the child and, if applicable, with the parent. The evaluation will link these two elements in order to test if staff capacity in childcare centres – at individual-level, centre-level and project-level - has an impact on child and parent outcomes and, if so, how.

A detailed set of instructions has been prepared for the Coordinators in each project to make sure that the process for recruiting the treatment group sample is consistent across the 11 projects. The full set of instructions are in Appendix Two.

Early Intervention Project was based on just 111 infants born between 1972 and 1977 of which 57 were in the treatment group and 54 in the control group. An overwhelming majority (98 percent) of the children who participated in the experiment were African-American. Another well-known programme, The Incredible Years Programme, is based on a series of evaluations with samples in the 25-35 range (see Webster-Stratton, 1981; Webster-Stratton, 1984; Webster-Stratton, 1994; Webster-Stratton and Hammond, 1997; Webster-Stratton, Reid and Hammond, 2004; Spaccarelli, Cotler and Penman, 1992).

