5.2 Comparison Group Sample

The comparison group sample is created in three stages. First, the catchment areas of the treatment group are identified in terms of demographic and socio-economic characteristics. For each NEYAI project, its catchment area is defined as the sum of the catchment areas of each childcare centre participating in the evaluation.

The data used to define these catchment areas is derived from the 2006 Census of Population, based on 'Small Areas' which have a minimum of 65 households and an average of 100 households; as such the data is almost 'street-level' and allows catchment areas to be defined precisely. This data will be expressed in terms of its deprivation score using the Pobal-Haase Index⁷². This data has the advantage that it is immediately available and, more to the point, the only data that allows areas to be defined in this way. The disadvantage is that while it is possible to match treatment and comparison areas in terms of deprivation scores, it is not possible to match them on other family characteristics which may be more relevant to this evaluation such as child and parent well-being, family functioning, neighbourhood and community factors. Nevertheless, the use of deprivation scores is the best available option and there are precedents for drawing comparison groups in this way, a notable example being the Sure Start evaluation⁷³.

Second, having established the level of deprivation in these catchment areas, a set of comparison areas will be identified which are matched as closely as possible to the treatment areas. In each of these comparison areas, childcare centres will be drawn from the Pobal database to match the

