childcare centres in the treatment group⁷⁴. The comparison group therefore is taken to represent the 'usual', 'average' or 'conventional' treatment provided by childcare centres to children and their parents. In other words, the basis of comparison in this evaluation is 'NEYAI treatment' versus 'treatment as usual' rather than 'NEYAI treatment' versus 'no treatment'. This also means that we explicitly exclude areas from the comparison group where it is known that other intensive childcare initiatives are operating such as Ballymun, Coolock and West Tallaght where there is already a significantly-above-average investment in early years programmes. This approach is reasonable and, in the circumstances, the best option available but it also needs to be acknowledged that 'treatment as usual' is an umbrella term which conceals more than it reveals since we do not know what 'usual treatment' actually means or how much it varies within as well as between childcare centres.

Third, the evaluators in collaboration with Pobal, will approach the City/County Childcare Committees and/or Partnership Companies in the identified areas and invite them to participate in the study. If agreeable, they will be asked to nominate someone who will act as a Study Coordinator in order to liaise with the selected childcare centres in their area. These Study Coordinators, whose role in the evaluation will be the same as the Project Coordinators in the treatment group, will be briefed by the evaluation team based on the same set of guidelines (see Appendix Two). Identical procedures will be used to select the sample of children.

The benefits to the City/County Childcare Committees and/or Partnership Companies of participating in this study are similar for those who are already participating in the NEYAI – excluding the benefit of implementing an NEYAI project - since each will receive study results for their area and will participate in a broader national study of childcare. Our expectation is that this benefit, in conjunction with the support of Pobal, will be sufficient to ensure their willingness to participate in the study and to adhere to its requirements.

6. Measurement Instruments

The dataset for the evaluation is generated through the following linked set of measurements:

- ✓ Child Questionnaire
- ✓ Parent Questionnaire
- ✓ Staff Questionnaire
- ✓ Template for describing each project intervention in the evaluation
- ✓ Data extraction on project area characteristics

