2. The timing of baseline data-collection is determined by the start-date of the intervention and the requirement that **no** intervention begins until the relevant baseline data has been collected. Coordinators will inform the Evaluation Team before baseline data-collection begins for the Staff Questionnaire, the Child Questionnaire and the Parent Questionnaire.
3. Coordinators will identify the childcare centres that are participating in the evaluation. Each childcare centre will be given a unique ID number from 1 upwards, preceded by the two letters identifying each project.
4. Coordinators will ask each childcare centre to compile a list of all childcare staff (excluding administrative and support staff). Each member of the childcare staff will be given a unique NEYAI Login Code by the Evaluation Team so that they can access the evaluation website: www.neyai-evaluation.ie. In order to ensure that childcare staff have full confidence in the confidentiality of the evaluation, the Coordinator will give the NEYAI Login Code to each individual childcare staff and assure them that no other member of staff knows this ID. This NEYAI Login Code must be used by staff to complete the Staff Questionnaire and the Child Questionnaire online. Coordinators may need to facilitate access to an internet-linked computer, in a private and confidential setting, where this is not available in the childcare centre so that the results of the Child Questionnaire can be entered on-line.
5. Coordinators will liaise with each childcare centre to generate a list of **all** children and their parents who are eligible to participate in the evaluation. To be eligible, the child must be aged three and a half years or over. This list will be compiled on an Excel spreadsheet based on a template provided by the Evaluation Team.

6. The Evaluation Team will supply each Coordinator with the randomly selected names of 35 children and their parents who will be invited to participate in the evaluation. An additional list of 10 randomly selected names will also be provided as replacements for those parents who do not consent to participate in the evaluation. This additional list is called the 'replacement list'.

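### Each project's 35 children are drawn with no step for childcare centre although the list shows the centre; sorting by centre first is a small, near-free improvement

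*Protocol*

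**What the plan says.** - **The draw.** Section 5.1: each project compiles one list of eligible children and parents, "from which the evaluation team will then draw a random sample of 35". Appendix Two, item 6 makes this operational: "The Evaluation Team will supply each Coordinator with the randomly selected names of 35 children and their parents".
- **Replacements.** Same item: "An additional list of 10 randomly selected names will also be provided as replacements". They stand in for parents who refuse. Nothing ties a replacement to the refuser's centre.
- **Centre is on the list.** Section 5.1: "The list of children and their parents prepared by each project will also indicate the childcare centres which are delivering the interventions", together with the staff member closest to each child.
- **Use of centre.** Section 5.1 links children to staff in order to "test if staff capacity in childcare centres" affects outcomes, "at individual-level, centre-level and project-level". Section 5.2 builds each project's area match from all its centres: "its catchment area is defined as the sum of the catchment areas of each childcare centre participating in the evaluation".
- **Comparison group.** Section 5.2: "Identical procedures will be used to select the sample of children".
- **Main model.** Under the fourth consideration in section 5, level 2 of the multi-level model is the project (its cluster of centres), not the single centre.

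**The concern.** The variable that would organise the draw is already on the sampling list, and the plan uses centres twice: to define the area match and to test staff capacity. Yet the draw as described runs across the whole project list. A centre can end up with no sampled child, or with one. The mix of centres varies by chance in both groups, and a refusal in one centre can be made good by a child from another.

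At stake is some precision in each project's mean and some information for the centre-level question. An analysis plan cannot mend this afterwards for a centre with no sampled child, because who is sampled is settled at the draw. Section 4.5 itself describes the sample as near the minimum needed, so a gain that costs almost nothing is worth taking.

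**Working it through.** **Plan's own figures.** 11 × 35 = 385 per group; 2 × 385 = 770; 5/35 = 14% attrition. For an effect of 0.2 SD, two-sided alpha 0.05 and power 0.80, the usual formula gives 393 per group, and 385 gives power 0.79. These reproduce, and nothing below alters them.

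**Assumptions.** The protocol gives no number of centres, centre sizes or ICC. I use lists of N = 120 in 5, 8, 10 or 12 equal centres, one very uneven list of 150 (40, 30, 25, 20, 15, 10, 6, 4), and ICC 0.05 to 0.20.

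**1. Chance that some centre has no sampled child, with an unsorted draw.** For one centre of size m, P(none) = C(N − m, 35)/C(N, 35). Inclusion–exclusion over centres gives the chance for any centre.
- Five centres of 24: 0.00008 for one centre, about 0.04% for any.
- Eight of 15: 0.0038, then 3%.
- Ten of 12: 0.0125, then 12%.
- Twelve of 10: 0.0270, then 29%.
- Uneven list (simulated): about 52%. The centre of 4 alone is missed with probability 34%.

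The chance that some centre has one child or none is about 24% for eight equal centres, 92% for twelve, and 95% for the uneven list.

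**2. Variance of a project mean, centres treated as random.** V = ICC × E[Σ(n_j/35)²] + (1 − ICC)/35. For twelve centres of 10:
- Unsorted draw: E[Σ(n_j/35)²] = 1/12 + (11/12)(85/119)/35 = 0.1020.
- Sorted systematic draw (eleven centres give 3 and one gives 2): (11 × 9 + 4)/1225 = 0.0841.
- ICC 0.05: V falls from 0.03224 to 0.03135, a cut of 2.8% (standard error 1.4%).
- ICC 0.20: V falls from 0.04327 to 0.03967, a cut of 8.3% (standard error 4.2%).

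Five centres of 24 at ICC 0.05 give a cut of 2.2% (standard error 1.1%). The range is therefore about 2% to 8% in variance and 1% to 4% in standard error.

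**3. The same, given the centres.** The between-centre term is ICC × E[Σ(n_j/35 − 1/12)²], which is 0.01871 × ICC unsorted and 0.00075 × ICC sorted. The within-centre term is (1 − ICC)(1 − 35/120)/35 = 0.02024 × (1 − ICC).
- ICC 0.05: 0.02016 falls to 0.01926, a cut of 4.5%.
- ICC 0.20: 0.01993 falls to 0.01634, a cut of 18%.

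With five equal centres at ICC 0.05 the cut is 4.1%. The range is about 4% to 18%.

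**4. Information on a centre-level predictor.** A centre with n children contributes n/(n × ICC + 1 − ICC). At ICC 0.10 a single child contributes 1.00, and each of four contributes (4/1.3)/4 = 0.77. Averaged over draws, the unsorted draw keeps about 94% to 98% of what the sorted draw gives, so sorting adds about 2% to 6%.

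**5. What sorting does not cure.** On the uneven list the sampling interval is 150/35 = 4.29, so the centre of 4 is still missed with probability 1 − 4 × 35/150 = 6.7% and never yields more than one child. A centre of 6 on a list of 120 expects 6 × 35/120 = 1.75 children, so it yields only one in 25% of draws.

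**The case against.** The strongest reply is that nothing here is wrong. A random draw from a complete project list is unbiased for the project mean, and 35 was chosen for a model whose level 2 is the project. The absence of a centre step is read from silence: the text says random, not simple random, and does not forbid ordering the list. All of this stands, except that section 5.1 refers to Appendix Two for the full instructions and those contain no centre step.

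A reader might infer that centres with one child or none wreck the centre-level test. The documents do not support that. A one-child centre still carries information, the loss overall is about 2% to 6%, and under section 6.3 all childcare staff in every participating centre complete the Staff Questionnaire whatever the child draw. A centre with no sampled child does, however, leave those staff data with no child outcome to link to.

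Including centre in the analysis could recover part of the precision. That too stands, though not for an empty centre.

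Strict same-centre replacement is also not workable as the guidelines are written: 10 reserve names over 8 to 12 centres is about one each, and Appendix Two, item 8 has reserve parents told in advance that they are reserves. The fix has to allow for this.

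**Conclusion.** The point holds as a small, near-free improvement to the sampling, not as an error or a source of bias. Its size rests on assumed centre lists and ICCs. The risk of an empty centre is negligible with five equal centres, 29% with twelve equal centres, and about 50% for a very uneven list. The gain is about 2% to 8% in the variance of a project mean with centres as random, about 4% to 18% given the centres, and about 2% to 6% in centre-level information.

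It would be a mistake to infer that the 385 and 770 totals are wrong, that the treatment comparison is biased by the draw, or that sorting guarantees usable numbers in every centre. The protocol supports none of these.

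**What to change.** In section 5.1 and Appendix Two, item 6, state that the evaluation team sorts each project's list by childcare centre and takes a systematic random draw of 35 (random start, interval of list length divided by 35). State that a refusal is replaced from the same centre where a reserve name is available, and otherwise by the next name on the random replacement list. Apply the same wording in the comparison areas.

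Every child keeps the same chance of selection, so no weights are needed, and no extra cases are required. The cost is a sort before the draw, a centre column on the reserve list and slightly more administration when a parent refuses. Very small centres may still yield one child or none. Guaranteeing two or more per centre would need a set minimum per centre with weights, which is a separate choice and not part of this fix.

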5.2 Comparison Group Sample

The comparison group sample is created in three stages. First, the catchment areas of the treatment group are identified in terms of demographic and socio-economic characteristics. For each NEYAI project, its catchment area is defined as the sum of the catchment areas of each childcare centre participating in the evaluation.

The data used to define these catchment areas is derived from the 2006 Census of Population, based on 'Small Areas' which have a minimum of 65 households and an average of 100 households; as such the data is almost 'street-level' and allows catchment areas to be defined precisely. This data will be expressed in terms of its deprivation score using the Pobal-Haase Index⁷². This data has the advantage that it is immediately available and, more to the point, the only data that allows areas to be defined in this way. The disadvantage is that while it is possible to match treatment and comparison areas in terms of deprivation scores, it is not possible to match them on other family characteristics which may be more relevant to this evaluation such as child and parent well-being, family functioning, neighbourhood and community factors. Nevertheless, the use of deprivation scores is the best available option and there are precedents for drawing comparison groups in this way, a notable example being the Sure Start evaluation⁷³.

Second, having established the level of deprivation in these catchment areas, a set of comparison areas will be identified which are matched as closely as possible to the treatment areas. In each of these comparison areas, childcare centres will be drawn from the Pobal database to match the

72 The Pobal-Haase Index was created by [name] and Jonathan Pratschke with funding from Pobal (Haase & Pratschke, 2005, 2008). The index is based on an understanding of affluence and deprivation, verified by confirmatory factor analysis, as having three dimensions which they refer to as: demographic profile, social class composition, labour market situation. The index combines these dimensions into a single score which is calculated at Electoral District level (3,409 units) and Small Area level (14,937 units). It has a mean score of zero and a standard deviation of ten; consequently nearly all scores are situated within three standard deviations of the mean, ranging between -30 and +30. Based on this index, areas are classified as 'disadvantaged' (score of -10 to -20), 'very disadvantaged' (score of -20 to -30), or 'extremely disadvantaged' (score of < -30). Further details at www.pobal.ie and www.trutzhaase.eu.

73 The first phase of the National Evaluation of Sure Start Impact Study compared children/families in 150 of the first 260 SSLP [Sure Start Local Programmes] with their counterparts living in 50 communities that did not have up-and-running SSLPs at the time they were studied but which were to have programmes shortly after data collection (that is, Sure Start-to-be communities). 'Overall data were collected on 12,575 nine-month-olds and 3,927 36-month-olds and their families in 150 SSLP communities, and on 1,509 nine-month-olds and 1,101 36-month-olds and their families in the comparison communities' (Belsky and Melhuish, 2007:136-137). In a subsequent follow-up, a sub-sample of the children in SSLP areas were compared to a sample of children from the Millennium Cohort Study (MCS) not living in SSLP areas. Propensity scoring was used to estimate if there was a significant difference between the two sets of areas in terms of '85 indices of deprivation and other areas characteristics obtained from administrative sources' (National Evaluation of Sure Start Team, 2010:11). The results of this analysis revealed that 'SSLP populations were, in general, more disadvantaged than the comparison population drawn from the MSC sample', and this in turn, 'posed problems in making comparisons between roughly equivalent NESS and MSC groups in order to evaluate the putative SSLP effects' (Ibid). The creation of a comparison group for the NEYAI evaluation is unlikely to generate such challenges because we expect to be able to find comparison areas that are a close match of treatment areas on the Pobal-Haase Index.

childcare centres in the treatment group⁷⁴. The comparison group therefore is taken to represent the 'usual', 'average' or 'conventional' treatment provided by childcare centres to children and their parents. In other words, the basis of comparison in this evaluation is 'NEYAI treatment' versus 'treatment as usual' rather than 'NEYAI treatment' versus 'no treatment'. This also means that we explicitly exclude areas from the comparison group where it is known that other intensive childcare initiatives are operating such as Ballymun, Coolock and West Tallaght where there is already a significantly-above-average investment in early years programmes. This approach is reasonable and, in the circumstances, the best option available but it also needs to be acknowledged that 'treatment as usual' is an umbrella term which conceals more than it reveals since we do not know what 'usual treatment' actually means or how much it varies within as well as between childcare centres.

Third, the evaluators in collaboration with Pobal, will approach the City/County Childcare Committees and/or Partnership Companies in the identified areas and invite them to participate in the study. If agreeable, they will be asked to nominate someone who will act as a Study Coordinator in order to liaise with the selected childcare centres in their area. These Study Coordinators, whose role in the evaluation will be the same as the Project Coordinators in the treatment group, will be briefed by the evaluation team based on the same set of guidelines (see Appendix Two). Identical procedures will be used to select the sample of children.

The benefits to the City/County Childcare Committees and/or Partnership Companies of participating in this study are similar for those who are already participating in the NEYAI – excluding the benefit of implementing an NEYAI project - since each will receive study results for their area and will participate in a broader national study of childcare. Our expectation is that this benefit, in conjunction with the support of Pobal, will be sufficient to ensure their willingness to participate in the study and to adhere to its requirements.

6. Measurement Instruments

The dataset for the evaluation is generated through the following linked set of measurements:

- ✓ Child Questionnaire
- ✓ Parent Questionnaire
- ✓ Staff Questionnaire
- ✓ Template for describing each project intervention in the evaluation
- ✓ Data extraction on project area characteristics
- ✓ Data extraction from the Growing Up in Ireland database

⁷⁴ We know from the Pobal database that there are 1,278 'community-based' childcare centres in the country, most of which are in disadvantaged areas.

- ✓ Template for observing the learning community

6.1 Child Questionnaire

The purpose of the Child Questionnaire is to assess the well-being of each child across a wide range of domains that are recognised as central to child development including: physical health; social competence; emotional maturity and regulation; language and cognitive skills; communication skills. The assessment of the child will be carried out in the childcare centre, jointly by the Childcare Leader and Childcare Worker who have a thorough knowledge of the child, and must know the child for at least a month. The questionnaire requires that answers are based on careful and reliable observation of all aspects of the child's development. Results of the Child Questionnaire are entered on-line by childcare staff. The Child Questionnaire was piloted in two childcare settings – none of which are part of this evaluation - and it can be completed in about half an hour.

The conceptual framework underpinning the Child Questionnaire is graphically illustrated in Figure 3. There is a detailed guide to every question in Appendix Three and the actual questionnaire is in a separate document. The left-hand-side of Figure 3 illustrates our theoretical understanding of the constituent elements of child well-being while the right-hand-side illustrates its likely determinants. This understanding, though not new or different from existing paradigms of child well-being, is a working hypothesis that will be tested against the data (see Section 9 below).

The main instrument within the Child Questionnaire is the Early Development Instrument (EDI). The EDI was developed at the Offord Centre for Child Studies at McMaster University in Hamilton, Canada. It has been validated as a measure of children's readiness to learn at school, based on data from over 16,000 Canadian children, collected in the spring of 1999⁷⁵. The EDI has been tested in both pre-school and school settings and there is a 'high inter-rater reliability' between the scores of early childhood educators and teachers⁷⁶. In Ireland, the EDI is being used to evaluate the Preparing for Life Programme by UCD Geary Institute⁷⁷ and has been used in a city-wide study of

75 Janus, Brinkman, Duku, Hertzman, Santos, Sayers, and Schroeder, 2007; Janus and Offord, 2007.

